5.3. Lifestyle Considerations

5.3.1. Meals and Dietary Restrictions

Participants must abstain from all food and drink (except water) at least 4 hours prior to any safety laboratory evaluations and at least 8 hours prior to dose administration. Water is permitted without restriction.

Part 1: The following requirements apply **ONLY** to Part 1, while the participants are confined in CRU:

- Breakfast will not be provided on Day 1.
- Noncaffeinated drinks may be consumed with meals and the evening snack.
- Lunch will be provided approximately 4 hours after dosing on Day 1. Dinner will be provided approximately 9 to 10 hours after dosing on Day 1.
- An evening snack may be permitted.
- The total daily nutritional composition, while confined, should be approximately 55% carbohydrate, 30% fat, and 15% protein. The daily caloric intake per participant should not exceed approximately 3200 kcal.

5.3.2. Alcohol, Caffeine and Tobacco

- All participants will abstain from alcohol for 24 hours prior to all outpatient visits. All participants may undergo an alcohol breath test or blood alcohol test at the discretion of the investigator. Participants in **Part 1** will abstain from alcohol for 24 hours prior to admission to the CRU and continue abstaining from alcohol during clinical confinement at the CRU. Participants may undergo an alcohol breath test at the discretion of the investigator.
- All participants will abstain from caffeine-containing products for 24 hours prior to all outpatient visits till the completion of infusion of the IP and necessary activities such as ECG, vitals, respiratory rate (RR). **Participants in Part 1** will abstain from caffeine-containing products for 24 hours prior to admission to the CRU and during confinement in the CRU.
- All participants will abstain from the use of tobacco- or nicotine-containing products for 6 hours prior to all outpatient visits and through the completion of infusion of the IP and necessary activities such as ECG, vitals, respiratory rate (RR). **Participants in Part 1** will abstain from the use of tobacco- or nicotine-containing products for 24 hours prior to admission to the CRU and during confinement in the CRU.

5.3.3. Activity

- Participants will abstain from strenuous exercise (eg, heavy lifting, weight training, calisthenics, aerobics) for at least 48 hours prior to each study visit requiring blood collection for clinical laboratory tests. Walking at a normal pace will be permitted.
- **Part 1:** Participants will be confined to the procedure room for the first 4 hours after dosing on Day 1 during continuous cardiac monitoring, except to use the bathroom. After this, if the equipment setup allows, participants may be ambulatory during the ECG monitoring period, but should not engage in strenuous activities. If equipment does not allow ambulation, appropriate accommodations will be made by the investigator site to facilitate continuous monitoring (eg, bedside urinals should be provided to accommodate participants' excretory needs).

5.3.4. Contraception

The investigator, or his or her designee, in consultation with the participant, will confirm that the participant has selected an appropriate method of contraception for the individual participant and his or her partner(s) from the permitted list of contraception methods (see [Appendix 4 Section 10.4.4](#)) and will confirm that the participant has been instructed in its consistent and correct use. At time points indicated in the [Schedule of Activities](#), the investigator or designee will inform the participant of the need to use highly effective contraception consistently and correctly, and document the conversation and the participant's affirmation in the participant's chart (participants need to affirm their consistent and correct use of at least 1 of the selected methods of contraception). In addition, the investigator or designee will instruct the participant to call immediately if the selected contraception method is discontinued or if pregnancy is known or suspected in the participant or partner.

In Part 1, females of childbearing potential enrolled are required to use a low user dependency, nonhormonal form of highly effective contraception for contraception method (such as an intrauterine device or surgical sterilization, as stipulated in [Appendix 4 Section 10.4.4](#)).

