Women of childbearing potential (WOCBP) will be eligible for participation if they agree and adhere to the contraception guidelines stipulated in this protocol ([Appendix 4: Contraceptive](#)), which include hormonally based contraception methods. Although reproductive safety data are not available for PF-07242813, there is no suspicion of human teratogenicity, genotoxicity, or clastogenicity based on the pharmacology of the compound that would preclude the inclusion of WOCBP using highly effective contraception into a controlled clinical trial. Compared to the contraception requirements in Part 1, the allowance for hormonal methods of contraception is justified by the accumulated safety and tolerability data from the SAD and MAD cohorts in Part 1 and will facilitate recruitment given that many patients with AD are of reproductive age and capacity. As an additional safety measure, WOCBP will be required to have a negative pregnancy test prior to randomization and at all study visits.

For both **Part 1 and Part 2**, Banked Biospecimens will be collected and stored for further analyses which may, for example, provide greater understanding of the study intervention.

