10.4.2. Female Participant Reproductive Inclusion Criteria

A female participant is eligible to participate if she is not pregnant or breastfeeding, and at least 1 of the following conditions applies:

- Is not a WOCBP (see definitions below in [Section 10.4.3](#)).

OR

- For Part 1: Is a WOCBP and using a contraceptive method that is highly effective (with a failure rate of $<1\%$ per year), with low user dependency and not hormonally based, as described below during the intervention period and for at least 60 days ($7 \times$ terminal half-life) after the last dose of study intervention, which corresponds to the time needed to eliminate any reproductive safety risk of the study intervention(s). The investigator should evaluate the effectiveness of the contraceptive method in relationship to the first dose of study intervention.
- For Part 2: Is a WOCBP and using a contraceptive method that is highly effective (with a failure rate of $<1\%$ per year), with low user dependency (including hormonally based methods), or, is using contraceptive method that is highly effective (with a failure rate of $<1\%$ per year) that is not of low user dependency (including hormonally based methods) together with a barrier method as described below during the intervention period and for at least 60 days ($7 \times$ terminal half-life) after the last dose of study intervention, which corresponds to the time needed to eliminate any reproductive safety risk of the study intervention(s). The investigator should evaluate the effectiveness of the contraceptive method in relationship to the first dose of study intervention.

The investigator is responsible for review of medical history, menstrual history, and recent sexual activity to decrease the risk for inclusion of a woman with an early undetected pregnancy.

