10.4.4. Contraception Methods

Contraceptive use by men or women should be consistent with local availability/regulations regarding the use of contraceptive methods for those participating in clinical trials.

Highly Effective Methods That Have Low User Dependency

1. Implantable progestogen-only hormone contraception associated with inhibition of ovulation. (*Prohibited for Part 1 healthy participants. Permitted only for Part 2 AD participants.*)
2. Intrauterine device.

3. Intrauterine hormone-releasing system. (*Prohibited for Part 1 healthy participants. Permitted only for Part 2 AD participants.*)
4. Bilateral tubal occlusion.
5. Vasectomized partner.
 - Vasectomized partner is a highly effective contraceptive method provided that the partner is the sole sexual partner of the WOCBP and the absence of sperm has been confirmed. If not, an additional highly effective method of contraception should be used. The spermatogenesis cycle is approximately 90 days.

Highly Effective Methods That Are User Dependent

6. Combined (estrogen- and progestogen-containing) hormonal contraception associated with inhibition of ovulation:
 - Oral;
 - Intravaginal;
 - Transdermal.
7. Progestogen-only hormone contraception associated with inhibition of ovulation:
 - Oral;
 - Injectable.
8. Sexual abstinence:
 - Sexual abstinence is considered a highly effective method only if defined as refraining from heterosexual intercourse during the entire period of risk associated with the study intervention. The reliability of sexual abstinence needs to be evaluated in relation to the duration of the study and the preferred and usual lifestyle of the participant.

One of the following effective barrier methods must be used in addition to the highly effective methods listed above that are user dependent:

- Male or female condom with or without spermicide;
- Cervical cap, diaphragm, or sponge with spermicide;
- A combination of male condom with either cervical cap, diaphragm, or sponge with spermicide (double-barrier methods).

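### Minor: in Part 2 the recurring contraception check can be passed on one method by women whom the protocol requires to use two

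*Protocol*

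**What the plan says.** **The requirement.** Protocol 10.4.2 gives a Part 2 woman of childbearing potential two routes: a highly effective method of low user dependency, or one "that is not of low user dependency (including hormonally based methods) together with a barrier method". Either applies as "described below during the intervention period and for at least 60 days" after the last dose. The method list in 10.4.4 repeats the second condition: "One of the following effective barrier methods must be used in addition to the highly effective methods listed above that are user dependent". Protocol 4.2.2 admits these women "if they agree and adhere to the contraception guidelines stipulated in this protocol". Hormonal methods are allowed in Part 2 (4.2.2, 6.5.2.2, 10.4.4), so the two-method situation can arise.

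**The check.** Table 3 schedules a contraception check at screening, at every visit from Day 1 to Week 16, and at early termination. Footnote d says only in whom it is done. Its content comes from 5.3.4: the investigator or designee reminds the participant about highly effective contraception and charts the conversation and her affirmation, with this standard: "participants need to affirm their consistent and correct use of at least 1 of the selected methods of contraception". The same section adds a duty between visits: "the investigator or designee will instruct the participant to call immediately if the selected contraception method is discontinued".

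**The concern.** The standard for the charted affirmation is lower than the rule that it is meant to support. For a woman on a single low-user-dependency method the two coincide. For a woman who must use a user-dependent method and a barrier they do not, and 5.3.4 makes no exception for her. A site that follows 5.3.4 to the letter can record a satisfactory check at every visit without learning that the barrier has been dropped.

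This is a participant-protection procedure in a first-in-human study for which 4.2 says no human reproductive safety data exist. A check of that kind should test the rule that it documents. What is at stake is the reliability of the adherence record and, to a small degree, protection against pregnancy. No efficacy or safety estimate depends on it.

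**Working it through.** The plan gives no figure to reproduce. The main check is a comparison of texts, followed by a rough bound on size.

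**Step 1. Requirement against check, for a Part 2 woman on an oral contraceptive plus condom**

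| Situation at a visit | 10.4.2 and 10.4.4 met? | 5.3.4 affirmation met? |
|---|---|---|
| Uses both | Yes | Yes |
| Pill only, condom dropped | No | Yes |
| Condom only, pill dropped | No | Yes, on the literal wording |
| Neither | No | No |

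The second row is the finding. The third is largely caught elsewhere: 6.5.2.1 has sites ask about concomitant medication at each visit and participants report changes to permitted medication, and stopping the pill clearly triggers the call-in duty.

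**Step 2. Does other text close the second row?**

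- The initial confirmation in 5.3.4 points to the 10.4.4 list, so the barrier should be chosen at entry. It does not reach later lapses.
- The call-in duty relies on the participant and speaks of one selected method, so it does not clearly cover the barrier.
- Table 3 footnote d adds no content.
- Pregnancy tests (4.2.2, 8.2.5, Table 3) find a pregnancy, not a lapse in contraception.

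No section requires both methods to be affirmed.

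**Step 3. Checks affected in Cohort 9**

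The single dose is on Day 1, so the 60-day minimum runs to Day 1 + 60 = Day 61. Scheduled post-dose checks in Table 3 fall on Days 8, 15, 29, 43, 57, 85 and 113, which is 7. Those on or before Day 61 are Days 8, 15, 29, 43 and 57, which is 5.

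**Step 4. Bound on the consequence**

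Inputs: a failure rate below 1% per year for a highly effective method (10.4.2), taken here as exactly 1% at a constant rate; 60 days (10.4.2); 24 participants randomized 2:1 (9.2.2).

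- Risk per woman on the retained method alone: 1 − 0.99^(60/365) = 0.00165, about 0.17%.
- Active-arm participants: 24 × 2/3 = 16.
- The number of women in this position is not given. Assuming a range of 0 to 16, expected pregnancies run from 0 to 16 × 0.00165 = 0.026, about 0.03.

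Sensitivity: 10.4.2 also describes its window as seven terminal half-lives. With the predicted 17 days (4.2.1) that is 7 × 17 = 119 days. All 7 checks would then fall inside it, the risk becomes 1 − 0.99^(119/365) = 0.00327, and the upper bound is 16 × 0.00327 = 0.052. The mismatch between 60 days and seven half-lives is a separate matter; it is used here only to show that the size stays small.

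**The case against.** The strongest reply is that nothing is really broken. The two-method rule in 10.4.2 and 10.4.4 is explicit, 4.2.2 ties participation to adherence, and dropping the barrier breaches the protocol whatever the participant affirms. Section 5.3.4 serves both parts of the study, and in Part 1 one method is enough. Its wording is a floor, so a site may ask about the barrier. It can also be read as at least one qualifying option from 10.4.4 with its attached conditions, which would include the barrier.

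Most of this stands, and it limits the finding. The rule is binding, and the generous reading is possible. But the plain words count methods, the floor is the only standard set for the charted affirmation, and nothing tells a site to go above it. What remains is a real gap in what must be verified.

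The bound also overstates the harm. The 0.17% is the whole risk on the retained method, not the increase from losing the barrier, which cannot be computed from the documents. The figure of 16 assumes that every active-arm participant is a woman on a user-dependent method who has stopped the barrier.

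A reader might infer more in three ways, none of them supported:

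- That 5.3.4 relaxes the rule to one method. It does not; it sets only what is affirmed at the check.
- That participants face a material pregnancy hazard. In the main scenario a method rated below 1% failure per year is still in use, 4.2 reports no suspicion of teratogenicity, and Cohort 9 is dosed once, after negative pregnancy tests (8.2.5).
- That the pregnancy-test schedule makes the gap worse. Protocol 4.2.2 says "WOCBP will be required to have a negative pregnancy test prior to randomization and at all study visits", whereas Table 3 marks fewer tests. That inconsistency is a separate point, because no test schedule would detect a dropped barrier.

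**Conclusion.** The point holds as a minor one. As written, the Table 3 contraception check can be passed and documented after a Part 2 participant has dropped a barrier that 10.4.2 and 10.4.4 require. Five scheduled post-dose checks in Cohort 9 fall within the 60-day minimum.

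The two-method requirement is unaffected and the safety consequence is small: at most about 0.03 expected pregnancies over 60 days. That bound rests on a constant 1% annual failure rate and the extreme assumption of 16 affected women. No endpoint, power calculation or analysis changes. The finding rests on the plain reading of 5.3.4 and on the absence of any other text that sets the content of the check.

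**What to change.** Make two changes in Protocol 5.3.4.

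1. In the affirmation, replace the reference to at least one selected method with: *all contraception methods required for that participant under Section 10.4.4 (including the additional barrier in Part 2 when the highly effective method is user dependent)*.
2. In the call-in instruction, replace the reference to the selected method being discontinued with: *any required contraception method is discontinued*.

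The cost is slightly longer counselling and chart documentation at visits that already take place. No visits, samples or staff are added.

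One related question is for the sponsor and is not part of this finding. Section 10.4.4 lists abstinence among the user-dependent methods ("Sexual abstinence is considered a highly effective method only if defined as refraining from heterosexual intercourse") and then applies the barrier sentence to that whole group. Whether abstinence should be exempt can be settled when 5.3.4 is edited.

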5.4. Screen Failures

Part 1: Screen failures are defined as participants who consent to participate in the clinical study but are not subsequently enrolled in the study. Screen failure data are collected and remain as source and are not reported to the clinical database. Individuals who do not meet the criteria for participation in this study (screen failure) may not be rescreened. However, for participants who have met the criteria for participation during screening but the screening falls outside 28-day window, they can be rescreened in this case.

Part 2: Screen failures are defined as participants who consent to participate in the clinical study but are not subsequently randomly assigned to study intervention. A minimal set of screen failure information is required to ensure transparent reporting of screen failure participants to meet the CONSORT publishing requirements and to respond to queries from regulatory authorities. Minimal information includes demography, screen failure details,

eligibility criteria, and any SAE must be documented in source and recorded in the CRF. Individuals who do not meet the criteria for participation in this study (screen failure) may be rescreened twice.

Delays in randomization of a participant (up to 1 week) related to receipt of primary or repeat laboratory results will not be considered protocol deviations.

6. STUDY INTERVENTION

Study intervention is defined as any investigational intervention, marketed product, placebo, medical device, or study procedure intended to be administered to a study participant according to the study protocol.

For the purposes of this protocol, study intervention refers to PF-07242813 and placebo, administered either intravenously or subcutaneously.

6.1. Study Intervention(s) Administered

Intervention Name	PF-07242813	Placebo
Type	Active Drug	Placebo
Dose Formulation	PF-07242813 100 mg/mL vial	Vial
Route of Administration	IV SC	IV SC
Use	Active	Placebo
IMP or NIMP	IMP	IMP
Sourcing	Provided centrally by the sponsor.	Provided centrally by the sponsor.
Packaging and Labeling	Study intervention will be provided in vials.	Study intervention will be provided in vials.

6.1.1. Administration

PF-07242813 and placebo will be administered intravenously or subcutaneously.

Following an overnight fast of approximately 8 hours, participants will receive study intervention (start time of infusion) at approximately 0800 hours (plus or minus 3 hours). For planned IV dosing (Cohorts 1-9 and 14), study intervention will be administered as an intravenous infusion over 15-30 min for dosing solution \leq 10 mL and 60 min for dosing solution $>$ 30 mL. In the case of mild infusion reactions, at the discretion of the investigator, the infusion may be interrupted and restarted at a slower infusion rate not to exceed a total administration duration of 90 minutes. The start and stop time of the infusion will be recorded in source document and CRF. Time 0 is the time when the study intervention infusion begins. The infusion rate and amount of volume infused will be recorded. For Cohorts 10-13, study intervention is planned to be administered subcutaneously. Each injection should occur at a different site on the abdomen, approximately 1 cm apart.

6.2. Preparation/Handling/Storage/Accountability

1. The investigator or designee must confirm appropriate temperature conditions have been maintained during transit for all study interventions received and any discrepancies are reported and resolved before use of the study intervention.

2. Only participants enrolled in the study may receive study intervention and only authorized site staff may supply or administer study intervention. All study interventions must be stored in a secure, environmentally controlled, and monitored (manual or automated recording) area in accordance with the labeled storage conditions with access limited to the investigator and authorized site staff. At a minimum, daily minimum and maximum temperatures for all site storage locations must be documented and available upon request. Data for nonworking days must indicate the minimum and maximum temperatures since previously documented for all site storage locations upon return to business.
3. Any excursions from the study intervention label storage conditions should be reported to Pfizer upon discovery along with any actions taken. The site should actively pursue options for returning the study intervention to the storage conditions described in the labeling, as soon as possible. Once an excursion is identified, the study intervention must be quarantined and not used until Pfizer provides permission to use the study intervention. Specific details regarding the definition of an excursion and information the site should report for each excursion will be provided to the site in the IP manual.
4. Any storage conditions stated in the SRSD will be superseded by the storage conditions stated on the label.
5. Study interventions should be stored in their original containers.
6. Staff will instruct participants on the proper storage requirements for take-home study intervention.
7. See the IP Manual for storage conditions of the study intervention, once diluted.
8. The investigator, institution, or the head of the medical institution (where applicable) is responsible for study intervention accountability, reconciliation, and record maintenance (ie, receipt, reconciliation, and final disposition records). All study interventions will be accounted for using a study intervention accountability form/record.
9. Further guidance and information for the final disposition of unused study interventions are provided in the IP manual. All destruction must be adequately documented. If destruction is authorized to take place at the investigator site, the investigator must ensure that the materials are destroyed in compliance with applicable environmental regulations, institutional policy, and any special instructions provided by Pfizer.

Upon identification of a product complaint, notify the sponsor within 1 business day of discovery as described in the IP Manual.

